Document Type:
Study Protocol with Statistical Analysis Plan (SAP)

Official Title of Study:
**Effects of Personalized Actionable Connected Extensible (PACE) Interventions
Among Patients With Chronic Kidney Disease**

NCT Number:
NCT06065501

Document Date:
05/20/2025

Subtitle:
Main Protocol – Taiwan Implementation Site

Sponsor:
National Cheng Kung University Hospital

Principal Investigator:
[name](c), RN

- Study Objectives: To examine the effectiveness Personalized Actionable Connected Extensible (PACE) Interventions for frailty among patients with CKD.
- Study Design: A randomized controlled trial with a single-blinded experimental design.
- Eligibility Criteria:
 1. The eligibility criteria included: (1) age 20 years or older; (2) diagnosis of CKD stage 1 to 5 for at least 6 months; (3) identified as frail; (4) the ability to communicate in Mandarin Chinese or Taiwanese; and (5) willingness to participate in the study.
 2. The exclusion criteria were: (1) receiving renal replacement therapy, (2) a history of mental illness, and (3) having reached TTM stage 5.
- Intervention/Comparator Descriptions:
 1. The PACE intervention involves using Line (technological devices) to establish a collaborative group with patients. The researchers will regularly provide reminders to chronic kidney disease patients regarding the importance of nutrition and exercise. They will also provide information on how to adhere to nutritional and exercise regimens, offering praise for consistent performance.
 2. Nurses provide routine education and consultation.
- Outcome Measures:
 1. Primary Outcome Measure: Tilburg Frailty Indicator (TFI)
 2. Secondary Outcome Measures: International Physical Activity Questionnaires (IPAQ, Taiwan Version); Health-promoting Lifestyle Behaviors (HPLP-II, Taiwan Version); Mini Nutritional Assessment Short-Form (MNA-SF, Taiwan Version)
- Statistical Analysis Plan:
 1. Descriptive Statistics: Mean \pm SD for continuous variables, Frequency (%) for categorical variables
 2. Comparative Analysis: Generalized estimating equations (GEE) are used to account for the non-independence of repeated measures over time within individuals and to control for potential confounding factors. The GEE models included main effects for group (intervention vs. control), time, and group-by-time interaction terms to examine whether there were statistically significant differences in outcome trajectories between the two groups over time. Covariates controlled in the models included age and gender. A significance level of 0.05 was used for hypothesis testing. All analyses were conducted using SPSS 25 version software.

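### Should eligibility require LINE access, given that PACE is described as running through LINE?

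*Combined protocol and SAP*

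**What the plan says.** Intervention/Comparator Descriptions, item 1, describes the channel in one sentence: "The PACE intervention involves using Line (technological devices) to establish a collaborative group with patients". The next sentence gives the content: "The researchers will regularly provide reminders to chronic kidney disease patients regarding the importance of nutrition and exercise". Information on how to adhere, and praise, follow. Those later sentences do not repeat the channel, and no telephone, face-to-face or other route is named. The comparator in item 2 is "Nurses provide routine education and consultation".

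Eligibility Criteria, item 1, lists five inclusion criteria. The first three are "1) age 20 years or older; (2) diagnosis of CKD stage 1 to 5 for at least 6 months; (3) identified as frail"; the last two are "the ability to communicate in Mandarin Chinese or Taiwanese; and (5) willingness to participate in the study". Item 2 lists three exclusions: "1) receiving renal replacement therapy, (2) a history of mental illness, and (3) having reached TTM stage 5". None of the eight mentions a device, LINE or the ability to use it, and there is no upper age limit.

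Statistical Analysis Plan, item 2, compares the arms by GEE, using "group-by-time interaction terms to examine whether there were statistically significant differences in outcome trajectories between the two groups over time", with age and gender as covariates and a 0.05 significance level. No analysis set is named, and no exclusion after allocation is described.

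**The concern.** An intervention delivered through a messaging app can work only in people who can be reached by it. The target population is frail, with the only age rule being "age 20 years or older", so some candidates may not use LINE. The language criterion concerns speech, and being willing to take part is not the same as being able to use an app. As written, a patient without LINE satisfies every criterion and can be allocated to PACE.

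If such patients are enrolled and PACE works, those in the PACE arm behave more like controls. The group-by-time contrast shrinks and power falls. A null result would then be hard to read, because an ineffective intervention and an undelivered one look alike. There is also a second risk. If unreached patients were removed from the PACE arm only, the two arms would no longer be comparable, and the direction of the bias could not be predicted.

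**Working it through.** **Inputs from the documents.** The significance level is 0.05 (Statistical Analysis Plan, item 2). Sample size, planned power, effect size, SD, allocation ratio and the share of patients without LINE are not stated, so there is no planned figure to reproduce.

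**Assumptions, for illustration only.** The test is two-sided. Power is 80% (or 90%) if every PACE patient receives the content. A share q = 10%, 20% or 30% of patients is unreached, equally in both arms. Unreached PACE patients get a fraction b of the benefit, with b = 0 or 0.5. One normally distributed contrast stands in for the GEE interaction.

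**Step 1. Signal with full delivery.** λ = 1.960 + z(power). For 80%, λ = 1.960 + 0.842 = 2.802. For 90%, λ = 1.960 + 1.282 = 3.242.

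**Step 2. Eligibility left as it is.** The as-randomised effect is multiplied by 1 − q(1 − b), so power = Φ(λ[1 − q(1 − b)] − 1.960). For example, with q = 0.2, b = 0 and 80% planned power: 2.802 × 0.8 − 1.960 = 0.281, and Φ(0.281) = 0.611.

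**Step 3. LINE criterion added, excluded patients not replaced.** The full effect returns but the sample shrinks to 1 − q of its size, so power = Φ(λ√(1 − q) − 1.960). For q = 0.2: 2.802 × 0.894 − 1.960 = 0.546, and Φ(0.546) = 0.707.

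| Starting from 80% power | q = 10% | q = 20% | q = 30% |
|---|---|---|---|
| As is, unreached gain nothing | 71.3% | 61.1% | 50.0% |
| As is, unreached gain half | 75.9% | 71.3% | 66.3% |
| Criterion added, no replacement | 75.7% | 70.7% | 65.0% |

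Starting from 90% with no benefit in the unreached, power is 83.1%, 73.7% and 62.1%.

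**Step 4. Break-even.** The two policies have equal power when 1 − q(1 − b) = √(1 − q), that is b = 1 − [1 − √(1 − q)]/q. For q = 0.1, 0.2 and 0.3 this gives 1 − 0.0513/0.1 = 0.49, 1 − 0.1056/0.2 = 0.47 and 1 − 0.1633/0.3 = 0.46. Below roughly half benefit the criterion gains power; above it, the criterion loses power.

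**Step 5. Price of holding power.** With the criterion, keeping the number randomised needs 1/(1 − q) = 1.11, 1.25 or 1.43 times the screening. Without it, if the unreached gain nothing, restoring power needs 1/(1 − q)² = 1.23, 1.56 or 2.04 times as many randomised.

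At q = 0 every loss is zero. Neither q nor b can be read from the documents.

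**The case for a change.** The strongest case for acting is that the gap is certain and closing it is cheap: one eligibility line and a short check before randomisation. If the unreached gain nothing, which is plausible when LINE is the only named channel, the criterion recovers power at every share in the table (for example 70.7% against 61.1% at 20%). Willingness does not establish ability, and one sentence committing to analysis by allocated arm would rule out selective removal.

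The textual part of this stands, as does the arithmetic under the no-benefit assumption. The rest is weaker.

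- **No benefit is an assumption.** The sentences on reminders, information and praise name no channel. Delivery of them through LINE is the natural reading, but it is an inference.
- **The share may be small.** A patient invited to a study whose intervention is a LINE group may well decline if unable to use it, and staff may recruit LINE users as a matter of course. In that case the criterion is an unwritten detail of practice.
- **The criterion has a cost.** It narrows the result to patients reachable by LINE and may under-represent older or frailer people.
- **Selective removal is not planned.** The model compares intervention with control and describes no exclusion. Analysing everyone in the allocated arm is the default reading of a randomised trial, and spelling it out would correct no stated rule. The unnamed analysis set is a general omission that does not depend on LINE.
- **It may be too late.** Eligibility and analysis are written partly in the past tense, although the intervention text looks forward. If enrolment is over, an eligibility criterion can change nothing.

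**Conclusion.** No change to the plan follows. LINE is the only channel named and eligibility is silent on access to it, but that alone does not make the design wrong. The stated objective is the effectiveness of PACE for frailty among patients with CKD. An as-randomised effect that includes people the app does not reach is a valid answer to that question. Dilution of this kind lowers the chance of detecting a benefit, but it does not by itself create a false one.

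The size for this trial is unknown. Under the assumed 80% power and 10% to 30% unreached, the loss without a criterion runs from about 4 points (10% unreached, half benefit: 80 − 75.9 = 4.1) to 30 points (30% unreached, no benefit: 80 − 50.0). Adding the criterion ranges from a clear gain (65.0 − 50.0 = 15 points) to a slight loss (65.0 − 66.3 = −1.3 points), depending only on what unreached patients receive. Requiring LINE access, providing another route, or accepting an effect that includes the unreached are three separate and defensible designs, and nothing in the documents shows that the third is a mistake. An analyst would keep all randomised patients in their allocated arm and describe LINE access and uptake where recorded, which is enough to interpret the result.

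### Does the analysis need to allow for correlation between PACE patients who share a LINE group?

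*Combined protocol and SAP*

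**What the plan says.** Intervention/Comparator Descriptions, item 1, gives the mode of delivery: "The PACE intervention involves using Line (technological devices) to establish a collaborative group with patients". The content follows: "The researchers will regularly provide reminders to chronic kidney disease patients regarding the importance of nutrition and exercise", together with information on keeping to the regimens and "offering praise for consistent performance". The text does not say how many LINE groups there are, how many patients each holds, or whether patients can read one another's messages. Item 2 gives the comparator: "Nurses provide routine education and consultation". No LINE group is described for it.

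Study Design reads "A randomized controlled trial with a single-blinded experimental design". The unit of randomization, the allocation ratio and the sample size are not stated.

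Statistical Analysis Plan, item 2, uses GEE to "account for the non-independence of repeated measures over time within individuals". The model has "main effects for group (intervention vs. control), time, and group-by-time interaction terms", where group means trial arm. On adjustment it says "Covariates controlled in the models included age and gender". LINE-group membership does not appear.

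**The concern.** A GEE clustered on the patient treats different patients as independent. Its robust standard error protects against a wrong working correlation within a patient, but not against correlation between patients. If PACE patients sit together in shared groups, receive the same reminders and see one another praised, their follow-up scores may move together. The effective number of independent units in the PACE arm would then be smaller than its number of patients. The standard error of the arm-by-time effect would be understated, and the test on the Tilburg Frailty Indicator (TFI), the primary outcome, would reject too often.

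The protocol's own language invites the question: it calls the group collaborative and the intervention connected. With the structure unstated, a reader cannot confirm that the patient is the right independent unit.

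**Working it through.** **No figure to reproduce.** The documents give no sample size, power, group size or intraclass correlation (ICC). The only numerical input is the 0.05 significance level, taken here as two-sided. Everything else below is assumed.

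**Assumptions.** Equal arms; equal total variance σ² at each visit; one baseline and one follow-up visit with correlation ρ; several PACE groups of size m; group-level correlation arising only after baseline and only in PACE; independent controls. ICC is defined on the follow-up score.

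**Formulas.**

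1. Variance of a patient's change: 2σ²(1 − ρ).
2. Group component of that change: ICC × σ². The ICC on the change score is therefore ICC / [2(1 − ρ)].
3. Design effect in the PACE arm: 1 + (m − 1) × ICC / [2(1 − ρ)]. In controls it is 1.
4. Averaging the two equal arms, the variance of the arm difference in change is inflated by V = 1 + (m − 1) × ICC / [4(1 − ρ)].
5. Actual type I error: 2 × [1 − Φ(1.96 / √V)].

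**One case in full.** m = 10, ICC 0.05, ρ = 0.5: V = 1 + 9 × 0.05 / 2 = 1.225; √V = 1.107; 1.96 / 1.107 = 1.771; type I error 7.7%.

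**Range.**

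| m | ICC | ρ = 0.3 | ρ = 0.5 | ρ = 0.7 |
|---|---|---|---|---|
| 5 | 0.01 | 5.2% | 5.2% | 5.4% |
| 10 | 0.02 | 5.7% | 6.0% | 6.8% |
| 10 | 0.05 | 6.9% | 7.7% | 9.5% |
| 20 | 0.05 | 9.0% | 10.7% | 14.3% |

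With m = 1 or ICC = 0, V = 1 and the error is 5%. The ρ = 0.7 column is harsher than its ICC suggests: an ICC of 0.05 on the follow-up score means 0.05 / (2 × 0.3) = 0.083 on the change score.

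**Simulation check.** With 40,000 runs, 5 assumed groups of 10, 50 controls, ICC 0.05 and ρ = 0.5, the patient-level robust test rejected 8.4% of the time. With ICC 0 it rejected 5.4%, so part of the excess over 5% is the small-sample behaviour of the robust test and not clustering. A comparison of group means with single controls, using Satterthwaite degrees of freedom, rejected 5.3% of the time on a median of 12.4 degrees of freedom. With 3 groups of 10 it rejected 6.0%, on a median of 7.3.

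**What the text supports.** Three readings fit the delivery sentence:

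- *One group for the whole arm.* Any group effect is inseparable from PACE, and no model can recover it.
- *Several shared groups.* The table applies, and a partially nested analysis would be informative.
- *A separate chat with each patient.* There is no clustering from this source.

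The noun is singular, and the actions described all run from researcher to patient. Nothing mentions exchange between patients. The several-groups reading is possible but is stated nowhere.

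**The case for a change.** The best case for a change is that it costs little. The researchers run the groups and can readily obtain the membership. One sentence would settle the reading, and a single partially nested sensitivity analysis on TFI would leave the GEE and the delivery as they are. At moderate assumed values (m = 10, ICC 0.05) the excess error is 1.9 to 4.5 percentage points, which would matter for a result near the threshold. The ambiguity is real and cannot be put down to redaction, since none is marked in these sections.

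Much of that stands. The description is incomplete, and the arithmetic is sound under its assumptions. What does not follow is a defect in the analysis. Bias requires several groups, patients sharing them, positively correlated outcomes and groups large enough for this to matter, and no section supplies any of these. The sensitivity analysis would do nothing under the single-group or one-to-one readings. Under the remaining one it would rest on few degrees of freedom and would leave the GEE as the main analysis.

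**Conclusion.** No change to the plan is needed. The gap is one of intervention description: the number, size and visibility of the LINE groups are not given. The people running the groups can fill it when they report the trial, and an analyst who learned that several shared groups existed could add a partially nested check without altering the main model.

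The GEE with the patient as the independent unit is a reasonable choice on what is written. The documents do not show that following it gives a wrong standard error. The possible effect runs from none to a type I error of 14.3% over the assumed values tabulated, a range too wide to say whether the issue matters here. It rests on assumed group size, ICC and baseline-to-follow-up correlation, on equal arms, and on clustering confined to PACE after baseline.

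### The GEE for the TFI omits baseline TFI as a covariate, so the group-by-time test is a valid but less precise difference in change, which age and gender barely alter

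*Combined protocol and SAP*

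**What the plan says.** The trial is described under Study Design as "A randomized controlled trial with a single-blinded experimental design". Outcome Measures makes the TFI the primary outcome, without a time point. Eligibility Criteria, item 1, requires patients to be "identified as frail", but names neither the instrument nor a cut-point.

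Statistical Analysis Plan, item 2 (Comparative Analysis), gives the model: "The GEE models included main effects for group (intervention vs. control), time, and group-by-time interaction terms". The stated purpose is to look for "statistically significant differences in outcome trajectories between the two groups over time". On adjustment it says "Covariates controlled in the models included age and gender". No other covariate is named, and equal baseline means across arms are not imposed. The item does not say whether the baseline score is one of the repeated responses. It is written in the past tense: "All analyses were conducted using SPSS 25 version software".

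**The concern.** In a randomised trial with a repeatedly measured score, the baseline value of that score is usually the covariate most strongly related to follow-up. The plan adjusts for two weaker ones instead. Two readings are possible.

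- **Reading A (ordinary).** Baseline is the first response, time is categorical, the link is identity, and age and gender enter as main effects. They are constant within a patient, so they shift all of that patient's responses equally and cancel from the group-by-time term. That term is the difference in change. It uses baseline, but with a coefficient fixed at 1 rather than estimated.
- **Reading B.** Only follow-up visits are responses. Age and gender then adjust the group main effect, but baseline TFI is not used at all.

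The stakes are power, and how far chance baseline imbalance moves the result. Bias is not at issue: regression to the mean from enrolling frail patients affects both arms alike and cancels. There is also a reporting risk. A reader told that the group-by-time result is controlled for age and gender would believe more than the model delivers.

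**Working it through.** The plan states no sample size, power or SD, so there is no figure of its own to reproduce.

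**Inputs.** From the documents: the model terms, the covariates, randomisation and the 0.05 level. Assumed: two-sided testing, equal allocation, one follow-up, large-sample formulas, unit variance at both times and baseline-to-follow-up correlation ρ in the unselected population. The variance of baseline among enrolled patients is v. If the TFI itself was the screen, baseline is truncated from below, and v = 0.486, 0.363 or 0.199 for a cut at −0.5, 0 or +1 SD. If another instrument was used, take v = 1.

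**Step 1: do age and gender cancel?** GEE was fitted to simulated data (100 patients, 3 visits, complete, identity link) with real age and gender effects. The group-by-time estimates were −0.29706 and −0.065773 (robust SE 0.152273 and 0.171912), with and without the covariates, under independence, exchangeable and AR(1) working correlation. They equal the raw differences in mean change. With about 20% of follow-up missing, the mean shift from adding age and gender was about 0.05 SE (exchangeable) and 0.16 SE (independence).

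**Step 2: is the change contrast valid?** In 2000 simulated trials per setting with 50 per arm, its mean was 0.498 (ρ = 0.5) and 0.501 (ρ = 0.7) for a true 0.5. Type I error was 4.6% and 4.9%.

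**Step 3: precision on reading A.** Per-patient variance of change is (1−ρ)²v + 1−ρ². With baseline as a covariate it is 1−ρ². Therefore

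- proportional gain G = (1−ρ)v / [(1−ρ)v + 1 + ρ];
- power, where the change contrast has 80%: Φ(2.802/√(1−G) − 1.960);
- shift in the change z-statistic per 1-SE baseline imbalance: √G, at any sample size.

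Worked case, cut at the mean, ρ = 0.5: 0.5 × 0.363 = 0.1815, and G = 0.1815/(0.1815 + 1.5) = 10.8%.

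| Screening | v | ρ | G | Power | z-shift |
|---|---|---|---|---|---|
| TFI, cut −0.5 SD | 0.486 | 0.4 | 17.2% | 87% | 0.42 |
| TFI, cut at mean | 0.363 | 0.4 | 13.5% | 85% | 0.37 |
| TFI, cut at mean | 0.363 | 0.5 | 10.8% | 84% | 0.33 |
| TFI, cut at mean | 0.363 | 0.7 | 6.0% | 82% | 0.25 |
| TFI, cut +1 SD | 0.199 | 0.7 | 3.4% | 81% | 0.18 |
| Other instrument | 1 | 0.3 | 35% | 94% | 0.59 |
| Other instrument | 1 | 0.5 | 25% | 90% | 0.50 |
| Other instrument | 1 | 0.7 | 15% | 86% | 0.39 |

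As a sample-size illustration without truncation, for an assumed difference of 0.5 SD, 80% power and ρ = 0.5, the change contrast needs 63 per arm and the baseline-adjusted one 48.

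**Step 4: precision on reading B.** The gain over a post-only comparison is ρ²v/(ρ²v + 1 − ρ²). With TFI screening this runs from 0.0318/(0.0318 + 0.84) = 4% (ρ = 0.4, v = 0.199) to 0.238/(0.238 + 0.51) = 32% (ρ = 0.7, v = 0.486). Untruncated it is 25% at ρ = 0.5 and 49% at ρ = 0.7. Age and gender may already recover part of this.

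**Step 5: which remedies work?** Adding baseline TFI as a main effect while baseline stays among the responses left the Step 1 estimates and SEs unchanged. In 300 simulated trials at a correlation of about 0.63, variance relative to the change contrast was:

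- 0.83 with baseline moved out of the responses and used as a covariate;
- 0.85 with a shared baseline mean and exchangeable correlation;
- 1.33 with a shared baseline mean and independence, where the model collapses to a post-only comparison.

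**The case against.** The strongest reply is that nothing here is an error. A group-by-time GEE is an accepted analysis, it is unbiased, and baseline adjustment is an efficiency preference. The gain cannot be fixed from the documents: if the TFI was the screen and ρ is high, it is as little as 3%. The plan does not state that baseline is a response. Age and gender are not wholly inert once visits are missing, least of all under independence. The past tense suggests the analysis may be done, which would leave only a sensitivity analysis. Finally, a model of post-baseline scores drops patients with no follow-up.

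Much of this stands, and it limits the point to precision with an uncertain size. It does not remove it. Both readings leave baseline information unused or partly used, and the improvement needs nothing beyond scores the trial should already hold. The shifts with missing data are small (0.05 to 0.16 SE), so the cancellation holds approximately. On reading B, main effects that are constant over time cancel from the group-by-time term too, so the caution about wording applies there as well. Patients with no follow-up carry no change score, so the change contrast gains little from them either.

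**Conclusion.** The concern holds. The planned primary comparison is valid but less precise than one adjusted for baseline TFI, and age and gender do almost nothing to the term being tested. On reading A the avoidable variance is about 3–17% with TFI screening (ρ 0.4–0.7) and 15–35% with another instrument (ρ 0.3–0.7). On reading B it is about 4–32% with TFI screening, and 25% and 49% at ρ = 0.5 and 0.7 without it. These ranges rest on assumed correlations, equal variances and assumed cut-points, none of which the documents supply. The cancellation itself requires an identity link and covariates entered as main effects only. The change is worth making because it is cheap; it does not rescue an invalid analysis.

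**What to change.** If the analysis has not been run:

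- State whether baseline is a response, together with the link and working correlation.
- Model post-baseline TFI on group, visit, group-by-visit, baseline TFI, baseline TFI-by-visit, age and gender, and report the adjusted between-arm difference at each visit.
- Treat IPAQ, HPLP-II and MNA-SF the same way, each with its own baseline. CKD stage is an optional further covariate.
- If a shared-baseline-mean model is preferred (no group main effect, baseline kept as a response), use a non-independence working correlation such as unstructured.
- Do not simply add baseline TFI to the present model, because that changes nothing.

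If results are already known, keep the planned model as primary and add the baseline-adjusted model as a labelled sensitivity analysis. Do not describe the group-by-time result as adjusted for age and gender.

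The cost is SAP wording and one changed SPSS model, or one extra analysis if results are known. No new data are needed, provided baseline scores were collected; the documents give no visit schedule to confirm this.

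### As described, the age and gender terms probably do not reach the group-by-time contrast, and CKD stage is not used; the cost is precision, not bias

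*Combined protocol and SAP*

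**What the plan says.** Under Comparative Analysis (Statistical Analysis Plan, item 2), the combined protocol and SAP specifies GEE models with group, time and "group-by-time interaction terms to examine whether there were statistically significant differences in outcome trajectories between the two groups over time". One stated reason for using GEE is "to control for potential confounding factors", and on covariates it says "Covariates controlled in the models included age and gender". No other covariate is named.

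Eligibility Criteria item 1 admits patients with "diagnosis of CKD stage 1 to 5 for at least 6 months". Item 2 excludes those "receiving renal replacement therapy". Study Design reads "A randomized controlled trial with a single-blinded experimental design", and no stratification factor is described.

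The documents do not say whether baseline is a level of the time factor, which link and working correlation apply, or how baseline TFI enters the model. They give no sample size, visit schedule, TFI standard deviation or expected effect.

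**The concern.** The plan presents its model as adjusted, but the effect it tests is a difference in change over time. A patient's age, gender and CKD stage at entry do not vary between visits. Entered as main effects, they shift that patient's whole profile up or down and leave the change alone. The adjustment may therefore be nominal for the one contrast that matters.

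What is at stake is efficiency. If change in TFI differs by kidney disease stage, that spread stays in the error term, and a chance difference in stage mix between arms goes uncorrected into the estimate. The obvious remedy, listing stage beside age and gender, would not help, because stage would cancel in the same way.

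**Working it through.** The plan has no figure to reproduce. The check takes the model form from Comparative Analysis; every other input below is an assumption.

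**1. Why main effects cancel.** With baseline as visit 0, a linear link and complete data, the group-by-visit coefficient at visit t equals

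(mean in PACE at t − mean in PACE at 0) − (mean in control at t − mean in control at 0).

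A covariate constant within patients adds the same amount, b × (its arm mean), to every visit mean in that arm. It drops out of both brackets whatever b is.

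**2. Numerical confirmation.** GEE with exchangeable correlation and robust SE; assumed 100 patients 1:1, 3 time points, within-patient correlation about 0.6, true effect −0.4, 150 runs per setting.
- Complete data, stage added as a main effect: the interaction estimate changed by 0.000 in every run, and its mean SE stayed the same (0.1766 and 0.1766 with stage explaining 20% of variance).
- 15% of follow-up values missing at random: the mean estimate moved by about 0.001 and the mean SE by less than 0.001, although single data sets moved by up to 0.08 (at 30%).
- In one further data set (40 per arm, 3 visits), the last-visit interaction was −0.1454 (SE 0.2114) with no covariates, with age and gender, and with stage added as a main effect. It became −0.0776 (SE 0.1853) only when stage was crossed with visit. This shows the mechanism; one data set says nothing about typical size.

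**3. Where adjustment does work.** In the 100-patient setting, with post-baseline visits only and the group difference as the contrast, adding stage lowered the mean SE from 0.197 to 0.193 (R² = 0.05) and from 0.197 to 0.166 (R² = 0.30). Mean estimates without stage were −0.38 to −0.42 against a true −0.40, so omission caused no material bias.

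**4. Gain from stage at an assumed 40 per arm.** R² is the share of outcome variance (in these runs, of change) that stage explains. The variance ratio, adjusted to unadjusted, is roughly (1 − R²) × (1 + small cost for estimating the stage effect). Simulation with 20,000 runs gave:

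| R² | Ordinal score | 3-level factor |
|---|---|---|
| 0 | about 1.015 | about 1.03 |
| 0.05 | 0.96 | 0.98 |
| 0.10 | 0.91 | 0.92 |
| 0.20 | 0.81 | 0.82 |

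Power from an assumed 0.80 is Φ(2.80/√ratio − 1.96). For the ordinal ratios:
- Φ(2.80/√0.96 − 1.96) = 0.82
- Φ(2.80/√0.91 − 1.96) = 0.84
- Φ(2.80/√0.81 − 1.96) = 0.88

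With the 3-level factor, the ratio of 0.98 at R² = 0.05 gives only 0.81.

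**5. Gain from baseline TFI.** With equal variances and baseline-to-follow-up correlation ρ, a change score has variance proportional to 2(1 − ρ), and a baseline-adjusted score to 1 − ρ². The ratio is (1 + ρ)/2: 0.75 at ρ = 0.5 and 0.85 at ρ = 0.7. Simulation at 40 per arm gave about 0.75-0.87.

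**6. Chance imbalance.** With 40 per arm and an assumed 30% in stages 4-5, the between-arm difference in that share has SD √(2 × 0.3 × 0.7/40) = 0.102. A 2-SD imbalance with an assumed 0.5 SD difference in TFI change by stage shifts the estimate by 2 × 0.102 × 0.5 = 0.10 SD. The SE of a difference in change is √(2/40) = 0.22 SD, so the shift is 0.10/0.22, under half a standard error.

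**The case against.** The strongest reply is that no error has been shown. Allocation is randomized, so leaving out a baseline factor does not bias the comparison. No stratification by stage is described, so no design factor has been dropped from the model. Nothing in the documents says that TFI change differs by stage. The chance imbalance in step 6 takes a roughly 1-in-20 event, and the unadjusted SE already allows for it. All of this stands, and it is why the point concerns precision only.

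A reader might infer more than the documents support:
- **That the PACE estimate is biased or confounded.** Randomization rules out systematic bias, and the plan's mention of confounding does not change that.
- **That imbalance will be large because one hospital runs the trial.** The number of centres is not stated, and chance imbalance depends on sample size rather than on the number of hospitals.
- **That stage is certainly on file for everyone.** This is likely, but since every stage is eligible, entry could be confirmed without recording the individual stage.
- **That the covariate list is closed.** The plan says the covariates included these two; it names no others.

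The reply does not remove the central point. Under the likeliest reading of the model, the adjustment the plan promises has no effect on the contrast it tests, and a readily available alternative does better.

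**Conclusion.** The point holds as one of precision. With baseline as a visit, a linear link and complete data, the age and gender terms leave the treatment contrast unchanged, and CKD stage plays no part. With moderate missingness at random the conclusion is practically the same.

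Adjusting for baseline TFI is likely to bring the larger part of the recoverable precision: a variance ratio of about 0.75-0.87 at assumed correlations of 0.5-0.7. The further gain from stage ranges from about 4% to 19% of variance for R² of 5% to 20%, against a loss of 1-3% if stage predicts nothing. These figures rest on an assumed 40 per arm and on correlations and R² values that the documents do not supply. The gains should not simply be multiplied, because what stage explains once baseline TFI is in the model may be smaller. Priority is low to moderate.

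**What to change.** Replace the covariate sentence with a full model statement:
- Analyse post-baseline TFI, and likewise each secondary outcome, by GEE with group, visit and group-by-visit.
- Adjust for the baseline value of that outcome, age, gender and baseline CKD stage, entered as one prespecified ordinal score.
- Define the effect as the adjusted group difference at a named follow-up visit, that is, the group term combined with the relevant group-by-visit term. The interaction among post-baseline visits alone should not be the test: with complete data, main-effect covariates cancel from it too, and it would miss an effect that is constant over follow-up.
- State the link, the working correlation and how time is coded.

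Crossing stage with visit in a model that keeps baseline as a visit also brings stage into the contrast, but that is a different model: it compares stage-adjusted change and does not regress on the baseline score. Choose one and prespecify it.

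The cost is a few lines of SAP text, one degree of freedom for the stage score and, if individual stage was not recorded, its retrieval from patient records. Eligibility need not change. The plan is partly in the past tense ("A significance level of 0.05 was used for hypothesis testing"). If outcomes have already been analysed, report this model beside the planned one and label it as added later.
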